1.0 Research Introduction

1.1 Purpose/Specific Aims

The goal of the study is to determine whether a high-dose corticosteroid regimen in patients admitted to the hospital with COPD exacerbations is associated with better clinical outcomes and at acceptable risk of adverse effects compared to a low-dose corticosteroid regimen. The study population includes patients ≥ 40 years-old with a ≥ 10 pack-years smoking history and a diagnosis of COPD, emphysema, or chronic bronchitis who present to the emergency room with increased dyspnea, increased sputum, or increased cough that requires admission to the hospital. We will perform a prospective, randomized, double-blinded study to determine if a high-dose corticosteroid regimen, which is already in use in clinical practice, decreases treatment failure compared to a low-dose corticosteroid regimen that is based on national consensus guidelines.

A. Objectives

Primary Aim: To determine if a high-dose corticosteroid regimen is associated with decreased rates of treatment failure compared to a low-dose corticosteroid regimen.

Secondary Aims:

- a) To determine if a high-dose corticosteroid regimen is associated with a reduced length of stay.
- b) To determine if a high-dose corticosteroid regimen is associated with better quality of life scores.

Tertiary Aim: To determine if a high-dose corticosteroid regimen is associated with an increased risk of short-term adverse effects.

B. Hypotheses / Research Question(s)

Protocol Number:

PI Name: [name]

Protocol Title: Determining Optimal Dose of
Corticosteroids in COPD Exacerbations: A
Pilot Study

3

RESERVED FOR IRB STAMP
DO NOT MODIFY THIS SPACE

IRB Form Version v120116

Our hypothesis is that high-dose corticosteroids are associated with a decreased rate of treatment failure, shorter length of hospital stay, and improved quality of life with similar risk of adverse effects.

1.2 Research Significance

Chronic obstructive pulmonary disease (COPD) is a preventable and treatable disease that is characterized by progressive airflow limitation that is not fully reversible. The airflow limitation is associated with an abnormal inflammatory response of the lung to noxious particles or gases, such as cigarette smoke.¹

Patients with COPD may come into the hospital with frequent acute exacerbations or flares of their disease, especially as the severity of their COPD increases.³ These acute exacerbations of COPD contribute significantly to morbidity and worsen quality of life.³ In patients with moderate to severe COPD, the in-hospital mortality rate was 9.9% with a 1-year mortality rate of 24.4% among those who were able to be discharged home.⁵

Oral or intravenous corticosteroids are recommended as an addition to other therapies in the management of COPD exacerbations.^{1, 6-9} A 2008 Cochrane review confirms that there is a significant reduction in the risk of treatment failure and rate of relapse within a month of treatment with corticosteroids. In the steroid treated group, the length of hospital stay was also significantly reduced with an increased rate of improvement in lung function and dyspnea.⁹ The FEV1 measured after bronchodilation increased by 90 mL daily up to day 5 of the hospital stay.⁶

While corticosteroids are required in the treatment of COPD exacerbations, the dose and duration of this treatment is still unclear and remains to be defined. Current consensus guidelines on the dose and duration of corticosteroid treatment vary. The Global Initiative for Chronic Obstructive Lung Disease (GOLD) recommends 30-40 mg of oral prednisolone daily for 7-10 days.¹ The Canadian Thoracic Society recommends oral or intravenous 25-50 mg of prednisone equivalent per day for 14 days; however, shorter treatment periods of between 7 and 14 days may also be effective.¹⁰ In the UK, the National Institute for Health and Clinical Excellence (NICE) recommends prednisolone 30 mg orally for 7-14 days; although, their consensus guidelines also state, "there is still debate about the optimal dose and duration."¹¹

Various studies have evaluated the route of administration, dose, and duration of corticosteroid treatment in COPD exacerbations. De Jong compared oral to intravenous administration of the same dose of prednisolone for 5 days and found no significant difference in treatment failure, length of hospital stay, or changes in spirometry and quality of life.¹² A large cohort study evaluated different doses and found that oral low-dose steroids (prednisone 20-80 mg daily) were associated with a decreased risk of treatment failure and length of stay compared to intravenous high-dose therapy (120-800 mg prednisone equivalent daily).¹³ A VA Cooperative study compared placebo to a 2-week and an 8-week corticosteroid taper. Rates of treatment failure were significantly higher in the placebo group than in the two glucocorticoid groups, but the 8-week regimen was not superior to the 2-week one.⁷ The

Protocol Number:

PI Name: [name]

Protocol Title: Determining Optimal Dose of
Corticosteroids in COPD Exacerbations: A
Pilot Study

4

RESERVED FOR IRB STAMP
DO NOT MODIFY THIS SPACE

IRB Form Version v120116

effectiveness of shorter corticosteroid regimens has been studied. A 10-day course of steroid treatment was more effective than a 3-day course in improving PaO₂, FVC and FEV₁, and symptom scores for dyspnea on exertion.¹⁴ Additionally, the REDUCE trial demonstrated non-inferiority of a 5-day regimen of prednisone 40mg daily when compared to an extended 14-day course.¹⁵

This research protocol will help further delineate the optimal dose of corticosteroids when given over a 10-day period consistent with prior research.

1.3 Research Design and Methods

We will perform a pilot study evaluating two commonly used doses of corticosteroids in the treatment of acute exacerbation of COPD. The study design is a randomized, double-blinded, prospective interventional trial. Our research staff will recruit, consent, and enroll patients admitted to the hospital with a diagnosis of COPD exacerbation. We will create randomization tables that will be provided to the research pharmacist. The research pharmacist will be telephoned, and they will randomly assign the patient to a low-dose or high-dose corticosteroid regimen. Medication will be prepared by a research pharmacist to maintain blinding. For in-hospital intravenous medication, the research pharmacist will provide to the nurses a container with the patient's name and medication without the dose. For oral medication, the pills will be inserted into a capsule and provided to nurses for in-hospital administration. At the time of discharge, a container filled with the remaining oral medication will be provided to the patient. Subjects receiving intravenous corticosteroid may be discharged to a nursing home before completion of the IV component of the regimen. Their regimen will be converted to oral equivalents, and a container will be provided to the nursing home. Copies of the patient brochure, signed consent, and written discharge instructions will also be provided. All data will be collected by our research staff via chart review of index and subsequent hospitalizations within the 30-day follow up period, as well as a phone interview with the patient at 30-days. The Clinical COPD Questionnaire will be administered during the phone interview. A patient is considered lost to follow-up if the data collection is not collected within 14 days after the 30-day follow-up date. In the event that we are unable to contact the patient, we will telephone the participant's personal medical doctor to confirm the patient's status. If necessary, we will obtain medical records for any outpatient physician visits made during the 30-day follow up period.

- i. Primary Outcome: The composite of treatment failure defined as death, intubation, re-admission for COPD exacerbation, or intensification of therapy (increased steroid use, change of antibiotic therapy) within a 30-day follow-up period.
- ii. Secondary Outcomes: Length of hospital stay and quality of life measured by Clinical COPD Questionnaire. The CCQ consists of 10 questions about the severity of COPD symptoms and limitation of activities over the prior week.
- iii. Tertiary Outcome: Composite outcome of short-term adverse effects. Defined as hyperglycemia, hypertension, adrenal suppression, psychiatric disturbance, infection, and gastrointestinal bleed that require a consultation, an invasive procedure, or initiation of a specific therapy.

Protocol Number:

PI Name: [name]

Protocol Title: Determining Optimal Dose of
Corticosteroids in COPD Exacerbations: A
Pilot Study

5

RESERVED FOR IRB STAMP
DO NOT MODIFY THIS SPACE

IRB Form Version v120116

Subject participation in the study ends after the 30 day follow up period. Study staff will also maintain contact with the patient's hospital physician and actively review the patient's chart during the index hospitalization for safety and adverse effect monitoring. Please see the study data collection form for additional specific data points that will be collected.

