1.9 Interviews, Focus Groups, or Surveys

A. Administration

The Clinical COPD Questionnaire (CCQ) will be administered by research staff during a telephone interview at 30 days following subject enrollment into the study. The patient will be provided this document in advance, at the time of hospital discharge, for reference.

B. Study Instruments

The CCQ is a validated tool utilized in prior literature to assess quality of life in patients with COPD. Higher scores indicate increased severity of symptoms and/or poorer quality of life, and are associated with increased mortality. ^{17, 18, 19, 20, 21}

In addition to the CCQ, research staff will query the patient about study endpoints during the follow-up telephone interview (re-admission, changes to steroid regimen, antibiotic therapy, and steroid-associated adverse effects that require a consultation, an invasive procedure, or initiation of a specific therapy).

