4.0 Research Data Source/s

4.1 Primary Data-Subjects and Specimens

Thirty day follow is obtained from patient/proxy via telephone contact (see data collection form).

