6.0 Research Data Protection and Reporting

6.1 Data Management and Confidentiality

A. Descriptive statistics (e.g., means, standard deviations, ranges, frequency distributions) will be examined for all relevant measures, and transformations of measures will be considered on the bases of distribution diagnostics and outlier analysis. The baseline characteristics of the patients in each of the two arms of the trial will be described and compared using chi-square statistics for categorical variables and t-tests or Wilcoxon statistics for continuous variables.

Protocol Number:

PI Name: [name]

Protocol Title: Determining Optimal Dose of
Corticosteroids in COPD Exacerbations: A
Pilot Study

15

RESERVED FOR IRB STAMP
DO NOT MODIFY THIS SPACE

IRB Form Version v120116

The intention-to-treat principle will be used for all randomized comparisons of study outcomes. The event rates for the primary, secondary, and tertiary clinical outcomes will be compared according to assigned corticosteroid group using chi-square statistics. The test for differences between groups in the composite primary outcome will be conducted at an alpha level of 0.05. The event rates for the individual clinical events and the additional pre-specified clinical events will be tested by treatment group with an alpha=0.01 to adjust for multiple comparisons. Event rates, absolute differences, and relative risks will be estimated, and 95% confidence intervals will be calculated.

B. This is a pilot study to establish an adequate sample size for a larger scale study as well as baseline event rates, thus a power analysis is not included in this submission.

C. Paper data will be stored in a locked filing cabinet in the Department of General Internal Medicine. A password-protected electronic database (that does not contain patient identifiers) will be stored on a HIPAA-compliant university computer at the same location. [name] will have sole access to this data until the study enters the data analysis phase. All study personnel are already trained in HIPAA procedures and have signed HIPAA confidentiality agreements as part of obtaining access to the Sunrise Clinical Manager system.

D. Collected data will be reviewed for quality and internal consistency by study staff after initial collection and before the data analysis phase of the study.

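### The day-30 CCQ has no rule for patients who die, so the quality-of-life comparison defaults to interviewed survivors and has no stated test that suits a score

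*Combined protocol and SAP*

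**What the plan says.** All references are to the combined protocol and SAP.

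- **Outcome.** Section 1.3 gives the secondary outcomes as "Length of hospital stay and quality of life measured by Clinical COPD Questionnaire".
- **Collection.** Section 1.3: "The Clinical COPD Questionnaire will be administered during the phone interview". Section 1.9 has it "administered by research staff during a telephone interview at 30 days following subject enrollment into the study". No baseline CCQ and no other CCQ time point is described.
- **Direction.** Section 1.9: "Higher scores indicate increased severity of symptoms and/or poorer quality of life, and are associated with increased mortality".
- **Respondent.** Sections 1.3 and 1.9 describe an interview with the patient. Section 4.1 says "Thirty day follow is obtained from patient/proxy via telephone contact (see data collection form". No section says whether a proxy may answer the CCQ.
- **Death.** It is a component of the primary composite (sections 1.3 and 1.6). Nothing links it to the CCQ.
- **Analysis.** Section 6.1.A: "The intention-to-treat principle will be used for all randomized comparisons of study outcomes". It then names chi-square on event rates for the primary, secondary and tertiary outcomes. Wilcoxon and t-tests are named only for baseline characteristics. There is no rule for CCQ scores that are absent through death or non-response, or that come from a proxy.

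**The concern.** A score taken once at day 30 exists only for patients who are alive and reached. Whether a patient survives to the call is itself an outcome after randomization, so survivors in the two arms need not be comparable even though the randomized groups were. Without a rule, the analyst will compare those who have scores, and that is not the intention-to-treat comparison the section promises.

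Two things are at stake. First, a death counts for nothing in secondary aim (b), and how to handle it would be decided after the data are in. Second, section 1.9 itself links higher (worse) scores to mortality. Deaths therefore tend to remove patients who would have scored badly, and the arm with fewer deaths keeps more of them. Its survivor mean is pushed upward, against the regimen with better survival. If the high-dose regimen had more deaths, the shift would run in its favour.

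The respondent question is a smaller, separate gap. The CCQ asks about symptoms and activity limits over the previous week, and a proxy's rating of these is not the same measurement as the patient's own.

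**Working it through.** The plan gives no CCQ effect size, SD, power or expected completeness, so it has no figure of its own to reproduce. What follows is an illustration.

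**Inputs from the documents:** N = 125 (sections 1.5 and 4.5), two arms, higher CCQ is worse.

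**Assumptions:** 1:1 allocation (62.5 per arm); CCQ SD 1.2; no true dose effect on the CCQ; correlation ρ of 0.3 to 0.7 between death risk and the CCQ a patient would have had; mortality of 10% or 15% in one arm against 5% in the other.

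**Step 1, survivor shift in one arm.** Under a bivariate normal model in which the fraction p at highest risk dies, the survivors' mean CCQ is lower than the whole arm's by SD × ρ × k(p), where k(p) = φ(z_p)/(1 − p) and z_p is the upper-p normal quantile.

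- p = 5%: k = 0.1031/0.95 = 0.1086
- p = 10%: k = 0.1755/0.90 = 0.1950
- p = 15%: k = 0.2332/0.85 = 0.2743

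**Step 2, bias in the arm difference** = 1.2 × ρ × [k(higher) − k(5%)].

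| Mortality | ρ = 0.3 | ρ = 0.5 | ρ = 0.7 |
|---|---|---|---|
| 10% vs 5% | 0.03 | 0.05 | 0.07 |
| 15% vs 5% | 0.06 | 0.10 | 0.14 |
| equal | 0 | 0 | 0 |

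In each non-zero cell the lower-mortality arm looks worse by that many points. A simulation under the same assumptions (400,000 per arm) gave 0.036, 0.050 and 0.072 for the first row and 0.057, 0.096 and 0.142 for the second, in agreement.

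**Step 3, compare with this pilot's precision.** SE = 1.2 × √(1/n₁ + 1/n₂), with n the survivors per arm.

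- 10% vs 5%: n = 56.25 and 59.375, so SE = 1.2 × 0.186 = 0.22
- 15% vs 5%: n = 53.125 and 59.375, so SE = 1.2 × 0.189 = 0.23

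The bias is therefore 0.031/0.223 = 0.14 to 0.139/0.227 = 0.61 of one standard error.

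**Step 4, a larger trial.** The bias does not depend on n. With an illustrative 500 interviewed per arm, SE = 1.2 × √(2/500) = 0.076. The 15% vs 5% row is then 0.060/0.076 = 0.8 to 0.139/0.076 = 1.8 standard errors.

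**The case against.** The strongest reply is that the bias is small, conditional and partly visible already. It needs a mortality difference, and the plan does not predict one. It is below one standard error in every scenario above, and section 1.5 disclaims adequate power. Section 6.1.A also compares individual clinical events by arm, so mortality should be reported in any case. All of that stands. It limits the numerical harm in this pilot, but it does not supply the missing rule. Section 6.1.A still has no method for a CCQ score, and this pilot's analysis is likely to be carried into the larger trial.

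Three stronger readings are tempting, and the documents do not support them.

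- **That 9.9% forecasts deaths here.** Section 1.2 reports "In patients with moderate to severe COPD, the in-hospital mortality rate was 9.9% with a 1-year mortality rate of 24.4"%, and 125 × 0.099 = 12.4 would suggest about 12 missing scores. That rate comes from a cited study of moderate to severe COPD. This trial sets no severity threshold and excludes patients who need intubation at recruitment or cannot consent, so its mortality may well be lower.
- **That the plan expects death to differ by arm.** The hypothesis in section 1.1 concerns treatment failure, a composite that could differ with equal mortality.
- **That proxies answer for the sickest.** No section says so. Section 4.1 is one general line pointing to a form that is not in the documents and may record the respondent. The direction of any proxy bias cannot be determined.

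It is also fair to say that worst-ranking deaths is one choice of estimand. A survivor analysis set beside mortality by arm is defensible too, which is why the change below shows both.

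**Conclusion.** The gap is real and worth closing, at moderate priority. As written, the quality-of-life comparison falls back on interviewed survivors, contrary to the stated intention-to-treat principle, and the one named between-arm test does not suit a score. The expected distortion is about 0.03 to 0.14 CCQ points against the arm with fewer deaths, and none if mortality is equal. The size rests on the assumed SD, correlations and mortality rates, none of which the documents give. The direction rests on the link between CCQ and mortality in section 1.9. The main loss is of definition rather than of numbers: deaths have no place in aim (b). On the respondent, the finding goes no further than that sections 1.3 and 1.9 do not match section 4.1.

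**What to change.** **Section 6.1.A.**

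- For the CCQ, replace chi-square with a Wilcoxon rank comparison by assigned arm in which patients who died by day 30 take the worst rank.
- Beside it, show the survivor-only CCQ difference, the number of deaths, and CCQ completeness, each by arm.
- Treat living patients without a CCQ as missing, not as worst-ranked, and add a simple sensitivity analysis for them. Worst rank covers deaths only, so this needs its own line.

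**Sections 1.3, 1.9 and 4.1.** Reconcile who may answer the CCQ, record the respondent, and show the result with and without any proxy scores. Barring proxies outright is a trade-off, because it could add missing scores.

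**Cost.** Wording changes, plus one recorded item (the respondent) if the data collection form does not already hold it. The ranked result is less direct to read than a mean difference in CCQ points, which the survivor-only difference shown beside it partly offsets.

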4.2 Subject Selection and Enrollment Considerations

A. Recruitment Details

Emergency room and medical staff will be informed about the study objectives, eligibility criteria, and protocol requirements prior to the initiation of the study. We will only recruit patients of physicians who are willing to follow the study protocol. Study staff will be notified of potential subjects that are identified by the emergency room staff and physicians. Study staff can also access a list of patients in the hospital who are being treated with prednisone or methylprednisolone to identify additional potential study subjects. Study staff will assess the medical records of each of the potential study subjects and, if they meet all eligibility criteria, approach the patient for consent. Eligible patients would have a diagnosis of COPD, emphysema, or chronic bronchitis with a presentation of increased dyspnea, increased sputum, or increased cough.

B. Source of Subjects

Subjects will be recruited from the RWJUH emergency room and general medical ward.

C. Method to Identify Potential Subjects

See section A above.

D. Subject Screening

Individuals will be screened for study inclusion by study staff using the eligibility and screening form.

▪ Inclusion Criteria

- Patients with a diagnosis of COPD, emphysema, or chronic bronchitis
- Age \geq 40 years-old
- Smoking history \geq 10 pack-years
- Presentation to the emergency room with increased dyspnea, increased sputum, or increased cough
- Admission to the hospital

▪ Exclusion Criteria

- Alternative diagnosis for cause of dyspnea, increased sputum or cough
- Patients who require intubation at time of recruitment
- Patients who are unable to give consent
- Patients who are pregnant or could be pregnant or are currently breast-feeding

Protocol Number:

PI Name: [name]

Protocol Title: Determining Optimal Dose of
Corticosteroids in COPD Exacerbations: A
Pilot Study

9

RESERVED FOR IRB STAMP
DO NOT MODIFY THIS SPACE

IRB Form Version v120116

- Women of child-bearing age who cannot use methods of contraception as described in the consent, including condoms, female condoms, cervical caps, diaphragms, and IUDs.
- Patients who were previously entered into the trial and are re-admitted to the hospital with a new COPD exacerbation.

A younger population is excluded because COPD is primarily an adult disease.

E. Recruitment Materials

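### Length of stay has no start point, no rule for in-hospital death and no test suited to a duration, so a difference between arms could not be read with confidence

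*Combined protocol and SAP*

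**What the plan says.** Secondary aim (a) in section 1.1 is "To determine if a high-dose corticosteroid regimen is associated with a reduced length of stay", so a shorter stay is read as benefit. Sections 1.3 and 1.6 name the secondary outcomes as "Length of hospital stay and quality of life measured by Clinical COPD Questionnaire" and do not define the first of them further.

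For analysis, section 6.1 states: "The event rates for the primary, secondary, and tertiary clinical outcomes will be compared according to assigned corticosteroid group using chi-square statistics". It names t-tests and Wilcoxon statistics only for comparing continuous baseline characteristics. It also states: "The intention-to-treat principle will be used for all randomized comparisons of study outcomes". Patients who die in hospital therefore stay in the comparison and need a value.

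Death is counted in the primary outcome, which is "The composite of treatment failure defined as death, intubation, re-admission for COPD exacerbation, or intensification of therapy" within 30 days. Nothing links it to length of stay. As background, section 1.2 says that in moderate to severe COPD "the in-hospital mortality rate was 9.9" percent.

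On timing of entry, section 4.2 says "Subjects will be recruited from the RWJUH emergency room and general medical ward", and lets staff search "a list of patients in the hospital who are being treated with prednisone or methylprednisolone". Some patients can therefore have been in hospital for a while before they are randomised.

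**The concern.** Three things are missing.

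- **A rule for death.** Without one, the natural chart value is admission to end of stay, and for a patient who dies the stay ends at death. An early death would then count as a failure in the primary outcome and as a short, favourable stay in aim (a).
- **A start point.** If the clock starts at admission, the outcome includes days that the assigned regimen cannot affect.
- **A test.** Chi-square on event rates does not apply to a number of days unless the stay is cut at some threshold, and none is given.

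These choices would have to be made after the data are in. Section 1.5 says the pilot is meant to supply outcome rates for sizing a later trial. A stay without a clock or a death rule gives no dependable SD or effect for that purpose.

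**Working it through.** The plan gives no effect size, SD or power for length of stay, so there is no figure of its own to reproduce.

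**Inputs from the protocol:** 125 patients (1.5, 4.5); 9.9% cited in-hospital mortality (1.2); 30-day follow-up (1.10).

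**Assumptions, not in the protocol:** arms of 62 and 63; log-normal stay with median 5 days and log-SD 0.6; mortality by arm; day of death; days in hospital before randomisation.

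**1. Expected deaths.** 0.099 × 125 = 12.4 in total, about 6 per arm. With the same 9.9% risk in both arms, binomial counts differ by 3 or more in about 45% of trials.

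**2. Shift caused by deaths.** The mean stay is 5 × exp(0.6²/2) = 5.99, about M = 6 days. Let D be the mean day of death and p the in-hospital mortality in each arm, with the same underlying stay in both. The mean in an arm is (1 − p) × M + p × D, so

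difference (higher- minus lower-mortality arm) = (p_high − p_low) × (D − M).

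| Mortality | D (days) | Difference (days) |
|---|---|---|
| 5% v 15% | 2 | 0.10 × (2 − 6) = −0.4 |
| 5% v 15% | 3 | 0.10 × (3 − 6) = −0.3 |
| 5% v 15% | 6 | 0.10 × (6 − 6) = 0 |
| 5% v 15% | 10 | 0.10 × (10 − 6) = +0.4 |
| 3% v 6% | 3 | 0.03 × (3 − 6) = −0.09 |
| 9.9% v 9.9% | any | 0 |

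D = 3 is what results if death falls uniformly over the stay the patient would otherwise have had.

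**3. Simulation, 3,000 or more trials per scenario.** The mean shifts agree with the table. The SD of the difference in means is about 0.7 day in the early-death cases. A two-sided Wilcoxon test at 0.05, scoring deaths at their day of death, rejects in about 8% of trials at 5% v 15% with D = 3, about 11% with D = 2, and about 5% with D = 6. It also rejects in about 5% at 3% v 6% with D = 3, and at equal mortality. With deaths ranked worst, rejection at 5% v 15% is about 15% to 16%, and deaths always count against the arm that has them.

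**4. Days before randomisation.** Whole days, equally likely between 0 and the stated maximum, were added to both arms alike. With no treatment effect, the mean difference stays at about 0 and rejection at 4% to 6%. For a stay 20% shorter in one arm, power is about 53% with no such days, 48% with 0 to 2 and 42% with 0 to 4.

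**The case against.** The strongest reply is that the protocol is silent and does not prescribe a bad rule. A reader might infer that the plan counts deaths as short stays and so favours the worse arm. The text does not say so. Sections 1.3 and 4.11 refer to a data collection form that is not among the documents and may record the stay in a particular way. The direction also depends on when deaths occur: with a mean day of death of 6 the shift vanishes, and at 10 it reverses. This stands, and the point is limited accordingly.

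The size also rests on a mortality difference. A three-fold difference is large for two regimens that the protocol says may both be regarded as standard of care. The cited 9.9% may be too high here, because section 4.2 excludes patients who need intubation at recruitment or cannot consent. This stands too; at 3% v 6% the shift is about 0.1 day, against an SD of about 0.7.

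A reader might also infer that days before randomisation can favour one arm. Randomisation balances them in expectation, so they cost precision only.

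Finally, death is already in the primary composite, and section 6.1 tests individual clinical events, so a large imbalance in deaths would be seen. That limits the harm, but it does not tell the analyst what stay to enter for a patient who died. Nor does it supply a test: one might assume that the Wilcoxon test in 6.1 covers length of stay, but it is named there only for baseline variables.

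**Conclusion.** The point holds as an omission. Aim (a) rests on an outcome with no clock, no death rule and no suitable test. If deaths are entered at their day of death, a mortality difference distorts the comparison by up to about 0.4 day either way in the 5% v 15% cases examined, in a direction set by death timing. With equal mortality there is no bias. Days before randomisation lower power, from about 53% to about 42% in the assumed 0-to-4-day case, without bias. The stay distribution, mortality by arm, day of death and days before randomisation are all assumptions. The missing test needs none of them: chi-square on event rates does not compare durations. For a secondary outcome of a pilot that disclaims adequate power, this is minor to moderate, and worth settling before the data are analysed.

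**What to change.** In sections 1.3, 1.6 and 6.1:

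- Define the outcome as days from randomisation to discharge alive, capped at day 30, with in-hospital death ranked worse than any stay.
- Assign the Wilcoxon rank-sum test to it in place of chi-square, with a median difference and 95% confidence interval. This is a new assignment, not a use of something already in the plan.
- Report in-hospital deaths by arm and total admission stay beside it, so that a reader can see whether a difference comes from deaths or from discharge times.

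Days alive and out of hospital to day 30, or time to live discharge with death as a competing event, would also be defensible. What matters is that one rule is fixed in advance.

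The cost is a few sentences. The dates of admission, randomisation, discharge and death should be available from study records and the charts already under review. The downside is small: the ranked outcome mixes death with stay, and is less direct than a mean number of days.
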